### 3.1.1 Drug-related adverse events (DRAE)

Drug-related adverse events (DRAE) will be defined as an AE or clinically significant abnormal laboratory value suspected to be related to therapy with BGJ398 (i.e., assessed as unrelated to disease progression, intercurrent illness, or concomitant medications), including those AEs and abnormal laboratory values that result in failure to meet the criteria for re-treatment or to begin a new cycle of therapy.

The criteria for defining DRAE are listed in (Table 3-1) using CTCAE v4.0.

Patients who experience a DRAE will have their therapy with BGJ398 interrupted and will be followed until the toxicity has resolved to CTCAE grade  $\leq 1$  or to the patient's baseline value. After recovery from the toxicity in question, if the investigator believes that it is in the patient's best interest to resume therapy with BGJ398, the patient may resume therapy at a lower dose level.

Prior to enrolling patients into a higher dose level, Grade  $\geq 2$  adverse events should be reviewed for all patients at the current dose level.

Table 3-1 Criteria for defining dose-modifications/interruptions for adverse events

TOXICITY	DRAE CRITERIA
Skipped/ delayed dose	The inability to administer BGJ398 on $\geq 75\%$ of scheduled treatment days during cycle 1 (i.e. $\geq 21$ days for a 28-days daily dosing schedule) due to unresolved adverse event of any grade and considered at least possibly, probably or definitely related to the study drug. Delay in 2 nd cycle administration due to failure of recovery from a possibly, probably or definitely related adverse event to grade $\leq 1$ or baseline by Day 43 (D28 of cycle 1 + 15 days), except for alopecia.
Blood/ bone marrow	Febrile neutropenia CTCAE Grade $\geq 3$ . Neutropenia CTCAE Grade $> 3$ for $> 7$ consecutive days. Thrombocytopenia  - CBC abnormalities CTCAE Grade 3 for $> 7$ consecutive days and/or with signs of clinically significant bleeding.  -CBC abnormalities CTCAE Grade 4. Anemia CTCAE Grade 4.
Renal/ genitourinary	Creatinine CTCAE Grade 1 for $> 7$ consecutive days and blood Pi $> 5.5$ mg/dL and/or blood tCa x Pi $> 55$ mg  /dL  and despite phosphorus lowering therapy for at least 14 days. Creatinine CTCAE Grade 2 for $> 7$ consecutive days. Creatinine CTCAE Grade $\geq 3$ .
Hepatic	Bilirubin CTCAE Grade 2 for $> 7$ consecutive days. Bilirubin CTCAE Grade $\geq 3$ . AST or ALT CTCAE Grade $\geq 3$ .
Pancreas	Pancreatitis CTCAE grade $\geq 2$ .

Abbreviated Title: BGJ398 in TIO

Version Date: 21MAY2019

TOXICITY	DRAE CRITERIA
	
Amylase/lipase (blood-high)
 
-CTCAE Grade <math>\geq 3</math> asymptomatic amylase and/or asymptomatic lipase not reversible to CTCAE Grade <math>\leq 2</math> within 7 days.

Cardiac	
QTcF interval <math>> 500</math>ms. Other CTCAE Grade <math>\geq 3</math>.

Constitutional	
Fatigue CTCAE Grade 3 for <math>> 7</math> consecutive days. Fatigue CTCAE Grade 4.

Ocular/visual	
Clinical evidence of corneal disorder/retinal disease of any grade (CTCAE grade <math>\geq 1</math>) including but not limited to corneal edema, abrasion, bullous/band keratopathy, inflammation/ ulceration, keratoconjunctivitis confirmed by ophthalmologic examination during any cycle. Any other ocular/visual toxicity CTCAE Grade <math>\geq 3</math>.

Gastrointestinal	
CTCAE Grade 3 or 4 nausea/vomiting and/or diarrhea despite the use anti-emetic and anti-diarrhea therapy, respectively.

Metabolic/ laboratory	
Hyperphosphatemia (blood-high)
 
-Blood Pi <math>> 7.0</math> mg/dL for <math>> 7</math> consecutive days despite phosphorus lowering therapy for at least 14 days.
 
-Blood Pi <math>> 9.0</math> mg/dL, despite phosphorus lowering therapy for at least 14 days.
 
-Blood Pi <math>> 10.0</math> mg/dL
 
Hypercalcemia (blood-high)
 
-Blood calcium CTCAE Grade 2 for <math>> 7</math> consecutive days.
 
-Blood calcium CTCAE Grade <math>\geq 3</math>.

Other	
Clinical evidence for any grade (CTCAE Grade <math>\geq 1</math>) of ectopic, de-novo-calcification within the soft tissue including the peri-articular spaces and vascular as well as visceral tissues (e.g. kidney, lung, stomach, myocard, etc.)
 
Any other CTCAE Grade 3 or 4 non-hematological toxicity except with following exclusions:
 
-Alkaline phosphatase CTCAE Grade <math>\geq 3</math>.
 
-Lymphocytopenia CTCAE Grade <math>\geq 3</math> unless considered clinically significant.

*Abbreviated Title: BGJ398 in TIO*

*Version Date: 21MAY2019*

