### 3.1.2 Dose Escalation

The starting dose of BGJ398 for all subjects not previously treated with BGJ398 will be 75 mg. This dose was based on studies investigating this drug's use in subjects with cholangiocarcinoma, as well as our two patients with TIO who have been treated on Novartis' signature trial. Patients previously treated with BGJ398 will be started on the last dose that they were taking prior to enrolling in this study, based on prior tolerability. While the two NIH patients treated on the Novartis Signature trial (6-9) were treated with 3 weeks on BGJ followed by 1 week off BGJ per cycle, our observations that hyperphosphatemia did not develop in these two subjects suggest that continuous BGJ therapy may be more efficacious in this population. Therefore, subjects will be treated with continuous BGJ398 therapy for six 28-day cycles. FGF23 levels will be measured every 2 weeks. If the FGF23 levels are not suppressed to less than 100 RU/ml on the 6-week outpatient labs, the dose of BGJ398 will be increased to 100 mg once daily after the 8-week NIH visit. The increased dose (100 mg) will be maintained for next 8 weeks. If the FGF23 levels continue to be greater than or equal to 100 RU/ml on the 14-week outpatient labs, the dose of BGJ398 will be increased to 125 mg daily after the-16 week NIH visit for the next 8 weeks. If a subject experiences a significant toxicity (DRAE), the medication will be held and restarted at the previous dose as described in section 3.1.1.

Sample dose modification table:

Dose Escalation Schedule	
Dose Level	Dose of BGJ398
Level 1	75 mg
Level 2	100 mg
Level 3	125 mg

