### **3.3 DOSE MODIFICATIONS**

For patients who do not tolerate the protocol-specified dosing schedule, dose adjustments are permitted to allow the patient to continue the study treatment. The following guidelines need to be applied:

- These changes must be recorded in the patient's medical records and eCRF.
- All dose modifications should be based on the worst preceding toxicity.

*Abbreviated Title: BGJ398 in TIO*

*Version Date: 21MAY2019*

- Following resolution of toxicity to baseline or  $\leq$  grade 1, treatment is resumed at lower dose of study drug as per Table 3.3.1. If treatment is resumed at the lower dose of study drug, and the same toxicity recurs with the same or worse severity, the patient must discontinue study treatment.

Table 3.3.1 Dose reduction table:

BGJ398 dose level	BGJ398 dose
Starting level (0)	75 mg po once daily
Dose level-1	50 mg po once daily
Dose level-2	25 mg po once daily

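### For the two Table 3-1 rows that hold BGJ398 at any grade (corneal or retinal disease; de-novo ectopic calcification), an unchanged grade 1 finding also meets the numeric restart threshold

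*Combined protocol and SAP*

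**What the plan says.** Section 3.1.1 of the combined protocol and SAP covers every drug-related adverse event (DRAE). "Patients who experience a DRAE will have their therapy with BGJ398 interrupted and will be followed until the toxicity has resolved to CTCAE grade" 1 or lower, or to the patient's own baseline. Restart is then a judgment: "After recovery from the toxicity in question, if the investigator believes that it is in the patient's best interest", treatment may resume at a lower dose level. Section 3.3 gives the same threshold: "Following resolution of toxicity to baseline or" grade 1 or lower, dosing resumes one step down Table 3.3.1 (75, 50, 25 mg). Neither section makes an exception for any row of Table 3-1.

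Two rows of Table 3-1 act at the lowest grade with no further condition:

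- The ocular row begins "Clinical evidence of corneal disorder/retinal disease of any grade", defines this as CTCAE grade 1 or above, and applies in any cycle once confirmed by eye examination.
- The row headed Other begins "Clinical evidence for any grade", again CTCAE grade 1 or above, and concerns de-novo ectopic calcification in soft, vascular or visceral tissue.

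Section 3.3 adds a stop rule: if drug is resumed at the lower dose "and the same toxicity recurs with the same or worse severity, the patient must discontinue study treatment". Section 3.1.2 sends patients who have a DRAE during dose escalation to the same place: "the medication will be held and restarted at the previous dose as described in section 3.1.1".

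**The concern.** The protocol treats these two toxicities most strictly on entry to a hold, so one expects the way out to require that the finding has gone. Instead the general threshold applies, and it admits the grade that caused the hold. A patient with a grade 1 finding that has not changed could be restarted, and the same finding would then be a DRAE again.

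At stake are patient safety and consistent conduct. Two investigators who both follow the text could handle the same patient differently: one restarts and holds again, another treats the persisting finding as recurrence and stops for good.

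Persistence at a low grade is plausible from section 11.1.2. About half of eye-related events resolved before the end of the source study, and later follow-up was inconsistent, so half is a minimum for resolution. In rats the slight corneal opacity was irreversible, although the associated keratopathy was reversible. In rats and dogs ectopic mineralization was only partially reversible. An eye disorder was the reason for 8 of 28 adverse-event discontinuations, although their grades are not given.

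**Working it through.** The plan gives no figure to reproduce, and no power or error rate is involved. The check compares two sets of grades.

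| Rule | Source | Grades covered |
|---|---|---|
| Hold, corneal or retinal disease | Table 3-1, Ocular/visual | 1, 2, 3, 4 |
| Hold, de-novo ectopic calcification | Table 3-1, Other | 1, 2, 3, 4 |
| Restart, all rows | 3.1.1 and 3.3 | 0 or 1, or baseline |

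1. **Overlap.** {1, 2, 3, 4} and {0, 1} share {1}. A grade 1 finding satisfies both rules at once.

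2. **The baseline alternative does not remove it.** For the eye row, exclusion criterion 4 bars current corneal or retinal disorder, so baseline is absence. For calcification, de-novo means the finding was not there before. But the two limbs are joined by *or*, so grade 1 is enough even when baseline is zero.

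3. **Recovery is not defined more tightly elsewhere.** The one place that measures recovery is the skipped or delayed dose row of Table 3-1, which counts a cycle 2 delay beyond Day 43 "due to failure of recovery from a possibly, probably or definitely related adverse event to grade" 1 or lower, or baseline. That is the same threshold. The permanent-withdrawal list in 3.10.1 has no eye or calcification criterion.

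4. **After restart.** The eye row applies in any cycle, so the unchanged finding qualifies again. Section 3.3 requires discontinuation if the toxicity *recurs* at the same or worse severity. A finding that never cleared has the same severity, but whether it has recurred is not stated.

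5. **Limits of the overlap.** An event of grade 2 or above in these rows must improve to reach grade 1, so only grade 1 findings are affected. Rows triggered only at grade 2 or above have no overlap. Rows triggered by a measured value, such as QTcF or phosphorus, are not expressed in grades.

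6. **Creatinine.** Its grade 1 trigger also lies inside the restart range. That trigger is conditional: more than 7 days, with phosphorus above 5.5 mg/dL and/or a calcium-phosphorus product above 55, despite at least 14 days of phosphorus-lowering therapy. Those conditions can change while creatinine stays at grade 1, so restart need not re-trigger the row at once.

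7. **Size.** A probability would need the rate of grade 1 findings in these rows at this trial's doses, the share that persist, and the share restarted unchanged. Section 11.1.2 gives 3.9% for grade 1 corneal events, from any cause, in another population, and says most eye disorders occurred at 100 mg or above. It gives no separate grade 1 retinal rate and no calcification rate, and nothing on restarts. No probability is offered here.

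**The case against.** The strongest reply is that the number is not the whole rule. Sections 3.1.1 and 3.3 speak of recovery and resolution, and an unchanged finding has done neither. Resumption is optional, rests on the investigator's view of the patient's best interest, and is at a lower dose. Eye examinations are monthly during the 24 weeks and can be added when clinically needed. All adverse events are followed to baseline or stabilization (7.1), the team generally discusses each patient weekly (7.7.1), and the monitoring committee meets about twice a year (7.7.4). Renal ultrasound is scheduled only at baseline and week 24, so renal calcification on the scheduled scan appears as treatment ends. Restart then matters mainly in the extension.

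Most of this stands, and it is why the point is modest. It does not remove the contradiction: none of these safeguards sets a different threshold. In the extension phase the stated minimum for eye examination is every three months (3.1.3).

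A reader might infer three stronger things that the documents do not support.

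- *That the protocol permits continued dosing on an active eye lesion.* It does not: the row applies in any cycle, so the finding calls for a further hold or a stop.
- *That only these two rows overlap.* Creatinine does too on grade, though conditionally.
- *That the grade 1 corneal toxicity among the four dose-limiting toxicities in 11.1.2 shows what to expect here.* It occurred in the 150 mg cohort; escalation here ends at 125 mg and new patients start at 75 mg.

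**Conclusion.** The point holds as a modest inconsistency in a safety rule. For the two rows triggered unconditionally at any grade, an unchanged grade 1 finding meets the numeric restart test and is a DRAE again on restart, and 3.3 leaves open whether it has recurred. This conclusion rests on the wording alone. It assumes only that the general threshold applies to every row, since no exception is written, and that baseline for these findings is absence.

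Its frequency cannot be estimated from the documents. It would be wrong to infer a flaw in the primary analysis: the endpoint, the analysis population and the exact confidence limits in 8.3 do not depend on this rule.

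**What to change.** Add to 3.1.1 and 3.3: for corneal or retinal disease and for de-novo ectopic calcification, the grade 1 alternative does not apply. BGJ398 may resume, at a lower dose, only after return to the patient's baseline, confirmed by ophthalmologic examination for the eye row or by repeating the test that detected the finding for calcification. Section 3.1.2 refers back to 3.1.1, so it needs no separate change. Nor does the creatinine row.

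Under this rule a finding has cleared before any restart, so a later one is plainly a recurrence and the stop rule in 3.3 can be applied without dispute. Whether to allow restart with a stable, inactive residual such as a corneal scar is an optional clinical decision. It would relax the 3.3 stop rule and is not part of this recommendation.

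The cost is a few sentences, longer holds for some patients, and possibly one unscheduled repeat test for calcification. Eye examination during a hold fits the existing provision for clinically indicated examinations in 2.5. A finding that does not clear would end treatment, and a patient who then withdraws counts as a failure (8.5). If that patient would otherwise have responded, 6/10 becomes 5/10 and the lower 95% limit in Table 8.4 falls from 26.2% to 18.7%, a drop of 26.2 − 18.7 = 7.5 percentage points. This cost is not wholly new, because the present text can also be read as requiring a permanent stop.

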### **2.2.2 Screening Visit**

Patients with a confirmed diagnosis of inoperable, metastatic, or non-localized TIO will be enrolled into this protocol by agreeing to and signing the informed consent and will undergo further eligibility screening (thoroughly evaluated based on the inclusion and exclusion criteria) at the NIH Clinical Center. This may be done as an inpatient or outpatient visit, at the discretion of the investigator and the subject. If eligible and the patient would like to begin drug immediately, the testing for the screening and baseline visits will be combined into a single inpatient visit. If not, the baseline visit and initiation of drug should occur within 6 weeks of the screening visit. Patients who have been previously treated with BGJ398 must be off BGJ398 for at least 2 weeks prior to the screening/baseline visit.

Procedures and tests during screening (if not combined with baseline visit) will include:

1. History
  - a. Detailed history of disease
  - b. Current medications including assessment of exclusionary medications/foods
2. Physical Exam
  - a. Height and weight measurement
  - b. Vital signs (pulse, blood pressure, temperature, and respiratory rate)
  - c. Physical examination
3. Blood tests
  - a. Blood chemistries: sodium, potassium, chloride, bicarbonate, creatinine, glucose, urea nitrogen, albumin, calcium, magnesium, phosphorous, alkaline phosphatase,

*Abbreviated Title: BGJ398 in TIO*

*Version Date: 21MAY2019*

- alanine aminotransferase (ALT), aspartate aminotransferase (AST), total bilirubin, direct bilirubin, LD, total protein, total CK, and uric acid
- b. Thyroid Stimulating Hormone (TSH) and Free Thyroxine (fT4)
- c. 25-OH vitamin D, 1,25 (OH)2-Vitamin D, intact PTH and FGF23 levels.
- d. Complete blood count (CBC): white blood cells (WBC), red blood cells (RBC), hemoglobin, hematocrit, mean corpuscular volume (MCV), red cell distribution width (RDW), and platelets.
- 4. Urine testing
  - a. Urine pregnancy test in females with childbearing potential.
  - b. Urinalysis: glucose, protein, urobilinogen, pH, hemoglobin, ketones, nitrite, leukocyte esterase, appearance, specific gravity, color, RBC, WBC, and squamous cells.
  - c. 24-hour urine for calcium, phosphorus, creatinine.
- 5. Imaging
  - a. FDG or Ga-DOTATATE PET/CT or Octreotide SPECT/CT if adequate study not done within the preceding 6 months.
- 6. Electrocardiogram to rule out exclusionary rhythm abnormalities.

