## **2.3 REGISTRATION PROCEDURES**

### **2.3.1 For Participating Site Registration: NOT APPLICABLE.**

## **2.4 RANDOMIZATION (OR STRATIFICATION) PROCEDURES: NOT APPLICABLE.**

## **2.5 BASELINE EVALUATION (MAY BE COMBINED WITH SCREENING VISIT):**

Subjects who elected not to initiate BGJ398 at the screening visit will return to the NIH for an inpatient admission within 6 weeks of the screening visit to begin BGJ398 treatment. At that time, the following procedures and tests will be performed prior to the first dose:

1. History
  - a. Interim history
  - b. Current medications
2. Physical Exam
  - a. Weight and height measurement
  - b. Arm span and sitting height will be measured at baseline and 24-week visits
  - c. Vital signs (pulse, blood pressure, temperature, and respiratory rate)
  - d. Physical examination
3. Blood tests
  - a. Blood chemistries: sodium, potassium, chloride, bicarbonate, creatinine, glucose, urea nitrogen, albumin, calcium, magnesium, phosphorous, alkaline phosphatase, alanine aminotransferase (ALT), aspartate aminotransferase (AST), total bilirubin, direct bilirubin, LD, total protein, total CK, 25 OH vitamin D and uric acid

*Abbreviated Title: BGJ398 in TIO*

*Version Date: 21MAY2019*

- b. Complete blood count (CBC): white blood cells (WBC), red blood cells (RBC), hemoglobin, hematocrit, mean corpuscular volume (MCV), red cell distribution width (RDW), and platelets.
  - c. Bone turnover markers - collagen type I C-telopeptide (CTX) and Procollagen I Intact N-Terminal (P1NP) (baseline, 12-week, 24-week, 36-week visits)
  - d. 25-OH-Vitamin D (baseline, 24-week, and 36-week visits)
  - e. 1,25-OH2-Vitamin D, intact PTH, FGF23
  - f. Two-hour oral glucose tolerance test (baseline and 8-week visit)
4. Urine testing
    - a. Urine pregnancy test in females with childbearing potential.
    - b. Urinalysis: glucose, protein, urobilinogen, pH, hemoglobin, ketones, nitrite, leukocyte esterase, appearance, specific gravity, color, RBC, WBC, and squamous cells.
    - c. 24-hour urine for calcium, phosphorus, creatinine (at monthly NIH visits)
    - d. Spot urine for calcium, phosphorus, creatinine (local laboratory visits only)
  5. Imaging
    - a. Renal ultrasound (baseline and 24-week visit)
    - b. Echocardiogram (baseline, 8-week, and 24-week visit) Patients with a decline in ejection fraction will be monitored monthly with serial echocardiograms for resolution.

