  6. Electrocardiogram (EKG) (screening and every 4-12 weeks depending on risk factors for long QTc)
  7. Questionnaires (described in section 3.5)
    - a. RAND SF36
    - b. PROMIS
  8. Rehabilitation Medicine Consultation
    - a. The Five Times Sit to Stand Test (lower extremity strength)
    - b. The grip strength test (hand dynamometer; upper extremity strength)
    - c. The Disabilities of Arm Shoulder and Hand Outcome Measurement (DASH).
    - d. Clinical rehabilitation evaluation (baseline, 24-week, and 36-week visits)
    - e. Six-minute walk test (baseline, 24-week, and 36-week visits)
  9. Placement of an indwelling catheter for frequent blood draws (baseline visit only)
  10. Ophthalmology Evaluation (baseline, monthly NIH visits while on BGJ398, 36-week, and as clinically indicated)
  11. With the first dose (time 0), the following tests are performed within the first 24 hours (baseline visit only):
    - a. Blood draw at time 0 and every 2 hours ( $\pm$  20 minutes) for phosphorous and creatinine
    - b. Spot urine at time 0 and every 2 hours ( $\pm$  20 minutes) for phosphorus and creatinine
    - c. Blood draw at time 0 and every 4 hours ( $\pm$  20 minutes) for FGF23, 1, 25 (OH)2-vitamin D, ionized calcium, iPTH.

*Abbreviated Title: BGJ398 in TIO*

*Version Date: 21MAY2019*

- d. Blood draw for pharmacokinetics at time 0 and 2, 4, 6, 8, 10 and 24 hours ( $\pm$  20 minutes) after the first dose.

All tests and procedures performed at the baseline visit will be repeated at the interval visits unless noted above. Pharmacokinetic samples will be repeated with fasting labs at the 4-week and 8-week visit. In patients with identifiable tumors and/or metastatic disease, the imaging study that best characterized their tumor(s) prior to BGJ398 will be repeated at the 24-week visit, if clinically indicated. See schedule of events in section 3.6.1 for more details.

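### Table 3-1 makes a persistent asymptomatic amylase or lipase rise a reason to interrupt BGJ398, but the repeated blood-test list in 2.5 names neither enzyme and 3.1.3 names no extension-phase analytes

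*Combined protocol and SAP*

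**What the plan says.** **Trigger.** The pancreas row of Table 3-1 has two entries. One is pancreatitis of grade 2 or higher. The other is a grade 3 or higher "asymptomatic amylase and/or asymptomatic lipase not reversible to CTCAE Grade" 2 or lower within 7 days.

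**Consequence.** Section 3.1.1 defines a drug-related adverse event (DRAE) to include a "clinically significant abnormal laboratory value suspected to be related to therapy with BGJ398". It then states: "Patients who experience a DRAE will have their therapy with BGJ398 interrupted". Follow-up runs until grade 1 or lower, or the patient's baseline value. Section 3.3 gives the same recovery standard ("Following resolution of toxicity to baseline or" grade 1 or lower), with resumption at a lower dose and permanent discontinuation if the same toxicity recurs at the same or worse severity.

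**Tests.** Section 2.5 itemises the baseline chemistries analyte by analyte, ending with "total bilirubin, direct bilirubin, LD, total protein, total CK, 25 OH vitamin D and uric acid". Its other blood items are the CBC, bone turnover markers, vitamin D metabolites, PTH, FGF23 and the glucose tolerance test. It adds: "All tests and procedures performed at the baseline visit will be repeated at the interval visits unless noted above". Section 3.1 says on-treatment labs follow the schedule of events in 3.6.1.

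**Extension phase.** Section 3.1.3 provides for monthly laboratory assessments in patients who resume drug at their maximum tolerated dose. It lists no analytes and does not refer to the schedule.

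**The concern.** A stopping rule works only if the measurement behind it is taken. This one is written for rises without symptoms, so nothing clinical would prompt the test, and the separate pancreatitis trigger does not cover it. If the schedule matches the 2.5 list, a patient with a persistent grade 3 rise could stay on drug, or have the dose raised to 100 or 125 mg on FGF23 results (section 3.1.2), through an event that the protocol says should interrupt treatment.

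The enzyme is not a remote concern for this drug. Apart from ocular events, section 11.1.2 names two grade 3 or 4 events seen in at least 5% of earlier patients: increased lipase (6.8%) and increased ALT (5.3%). ALT is on the 2.5 list; lipase, the more frequent, is not.

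**Working it through.** The plan gives no figure to reproduce on this point. The main check is a comparison of texts, and the arithmetic only gives a sense of scale.

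**1. Laboratory triggers in Table 3-1 against the 2.5 list**
- Named in 2.5: platelets, hemoglobin, creatinine, phosphorus, calcium, bilirubin, AST and ALT.
- Not named, but obtainable from a differential on the listed CBC: neutrophils, and lymphocytes (which count only when clinically significant).
- No test in the list: amylase and lipase.

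Elsewhere in the readable text, lipase appears only in the toxicity summary in 11.1.2, and amylase does not appear.

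**2. The schedule of events**
The readable part of 3.6.1 begins at the FGF23 row, and the chemistry rows above it are lost. Each readable row corresponds to an item in 2.2.2 or 2.5, so nothing visible suggests that the schedule adds analytes. This does not settle what the lost rows contain. The visible header ends at week 36.

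**3. Timing**
Scheduled draws are nominally 14 days apart. A criterion of failure to improve within 7 days cannot normally be applied from them; it needs a repeat draw. Section 7.1 requires clinically significant abnormal results to be followed but sets no interval.

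**4. Scale**
Inputs: 6.8% with grade 3 or 4 increased lipase (11.1.2), 207 patients treated (11.1.2), N = 10 (8.5).
- Expected patients with such a rise: 10 × 0.068 = 0.68.
- Chance of at least one: 1 − (1 − 0.068)^10 = 0.506. With N = 9 it is 0.469.
- Uncertainty in the rate: 0.068 × 207 = 14.08, so 14 of 207 is inferred. The exact 95% interval is 3.75% to 11.09%, and 1 − (1 − p)^10 then runs from 0.317 to 0.691.
- The documents do not give the share s of these rises that would be persistent, clinically significant and suspected to be drug-related. Under assumed shares, 1 − (1 − 0.068s)^10 is 0.066 for s = 0.10, 0.158 for s = 0.25 and 0.292 for s = 0.50.
- Dose: 164 of the 207 patients (79%) were in expansion arms at 125 mg. Drug-naive patients here start at 75 mg and may rise to 125 mg.

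**The case against.** **The decisive rows cannot be read.** Section 3.1 sends on-treatment labs to the schedule of events, and its chemistry rows may list both enzymes. A reader might infer that the protocol never measures them. The documents do not support that: what can be shown is that the 2.5 list omits them. If the schedule includes them, the on-treatment point shrinks to aligning 2.5 with it.

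**The lists are not exhaustive.** Exclusion criterion 10 uses the neutrophil count, yet the CBC components in 2.2.2 include no differential. Table 3-1 also has a catch-all row for other grade 3 or 4 non-hematological toxicity, so it was not built to match the test lists one for one. This is fair and lowers confidence. It does not fully answer the point, because a differential comes from a listed test, whereas no listed test yields amylase or lipase. An investigator may order either enzyme, but an asymptomatic rise gives no reason to.

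**The 51% is not the DRAE risk.** A reader might take it as the chance of a missed stopping event. It covers any grade 3 or 4 lipase rise regardless of cause, mostly at the top dose and in cancer patients. None of the four dose-limiting toxicities in 11.1.2 was pancreatic, and the same section calls most adverse events mild to moderate, reversible and unrelated to drug.

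**A baseline value is not essential.** A reader might infer that recovery could not be judged without one. Grade 1 or lower is sufficient on its own under 3.1.1 and 3.3, although that too requires the enzyme to be measured.

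**Extension labs.** The lack of named analytes in 3.1.3 affects every test, and its statement that monitoring continues can be read as carrying the earlier panel forward. That reading is reasonable but not written down.

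**Conclusion.** The point holds in a limited form. The repeated 2.5 list contains no test for an event that Table 3-1 makes a reason to interrupt treatment, 3.1.3 does not say which tests the extension labs include, and no repeat is set at the interval the criterion needs. Whether the enzymes are actually unmeasured during the 24 weeks depends on schedule rows that could not be read.

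Severity is low to moderate, with medium confidence. About 51% for at least one grade 3 or 4 lipase rise in 10 patients (32% to 69% over the interval for the inferred 14 of 207) is an upper guide that assumes the earlier rate carries over to this population and dosing. The DRAE rate would be lower and is not given; 7% to 29% is what assumed shares of 10% to 50% would produce. The definition and analysis of the primary endpoint are unaffected.

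**What to change.** 1. Check the chemistry rows of the schedule of events for amylase and lipase.
2. Add both to the 2.5 chemistry list, at the pre-dose baseline and the monthly on-drug NIH visits, and to the schedule if they are absent.
3. State in 3.1.3 that the monthly extension labs use the same panel.
4. Require a repeat about 7 days after any grade 3 or higher value, so that the criterion can be applied.

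The Table 3-1 criterion stays as it is. The screening list in 2.2.2 need not change, because no eligibility criterion uses either enzyme and baseline tests are taken before the first dose.

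**Cost.** Two assays, normally on blood already drawn, and an occasional unscheduled repeat draw. If a separate 4 mL tube were needed (assumed, the volume Table 5.1 gives for FGF23) at the 7 NIH visits from week 0 to week 24, the total would go from 584 to 584 + 7 × 4 = 612 mL. The 8-week maximum would go from 265 to at most 265 + 3 × 4 = 277 mL, against the 550 mL limit in section 5; each repeat adds a further 4 mL. Detecting asymptomatic rises may also cause some extra interruptions or dose reductions, and under 3.3 a recurrence means discontinuation. In 10 patients that could matter for efficacy, but it is what the protocol's own rule calls for.
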